2.3 SUBJECT EXCLUSION CRITERIA (ADULT AND PEDIATRIC POPULATIONS)

Exclusion criteria apply to both the adult and pediatric populations.

1. **Adult subjects:** In the opinion of the investigator, subject is mentally or legally incapacitated at entry into PN017.

Pediatric subjects: The subject has significant emotional problems or a clinically significant psychiatric disorder that may interfere with participant treatment, assessment, or compliance with the protocol.

2. Subject has received HCV therapy after completion of the prior treatment study and before entry into PN017.
3. Starting with AM 03: subjects who failed therapy due to re-infection, defined as:
 - an HCV RNA sample with a different genotype than the baseline genotype in the prior treatment study, or

- an HCV RNA sample determined to be reinfection by phylogenetic analysis with comparison to the baseline sequence in the prior treatment study.

4. Starting with AM 03: subjects who failed therapy in the prior treatment study and received retreatment with HCV therapy.

2.4 STUDY DESIGN AND DURATION

2.4.1 Summary of Study Design

This is a multicenter long-term follow-up study for subjects previously treated with at least one dose of GZR in a Merck-sponsored clinical study.

2.4.1.1 Adult Population

Prior to AM 03, all HCV-infected adult subjects previously treated with GZR in a Merck-sponsored clinical study (parent study) were eligible for enrollment into PN017.

Starting with AM 03, several significant changes have been made to the study design and duration:

1. New enrollment will be limited to those who failed therapy in the prior treatment study.
2. Subjects in PN017 with virologic failure at FW24 in the prior treatment study will continue for 3 years of follow-up (other than PN052 subjects) or 5 years of follow-up (PN052 subjects).
3. Subjects (other than PN052 subjects) in PN017 who entered with HCV RNA <LLoQ were discontinued after the next scheduled visit.
4. Subjects who receive a new HCV therapy regimen during PN017 will be discontinued.
5. The enrollment window is 3 months after the last visit in the prior treatment study.

There are a total of 7 study visits (11 study visits for PN052 subjects) and, as needed, a viral confirmation visit.

2.4.1.2 Pediatric Population

The anticipated duration is 3 years for pediatric subjects. Subject enrollment is limited to subjects from PN079 who experienced virologic failure associated with 1 or more treatment-emergent RASs present at FW12. There are a total of 7 study visits and, as needed, a viral confirmation visit. Pediatric subjects who receive a new HCV therapy regimen during PN017 will be discontinued.

2.4.2 Treatment Plan

Not applicable.

2.5 LIST OF EFFICACY/PHARMACOKINETIC/IMMUNOGENICITY MEASUREMENTS

The following measurements are applicable for the adult and pediatric populations.

HCV Genotype

Samples will be genotyped using the Food and Drug Administration (FDA) approved Abbott HCV Real Time Genotype II assay which detects HCV GT1a, 1b, 2, 3, 4, 5, and 6 through the use of genotype-specific fluorescent-labeled oligonucleotide probes in a real-time reverse transcriptase-polymerase chain reaction (RT-PCR) assay. The RT-PCR reaction uses 3 sets of HCV specific amplification primers targeting the conserved 5' untranslated region (for all genotypes) and NS5B regions from GT1a and 1b. The assay has accuracy of >96% for GT1, 1a, 1b, 2, 3 and 4, 89% for GT5 and 83% for GT6 with 100% specificity in HCV serologically negative plasma samples. Phylogenetic analyses will be performed using sequences for NS3/4A, NS5A and NS5B to ensure accurate assignment of sample genotype/subtype.

HCV RNA

HCV RNA in plasma will be measured using a COBASTTM AmpliPrep/COBASTTM TaqmanTM HCV Test, v2.0 ® assay with a LLoQ of 15 IU/mL. HCV RNA definitions are presented in [Table 1](#).

Table 1

HCV RNA Definitions

Abbreviation	Definition	HCV RNA Level
TND	Target not detected	HCV RNA not detected
TD(u)	Target detected, unquantifiable	HCV RNA < LLoQ
TD(q)	Target detected, quantifiable	HCV RNA ≥ LLoQ

HCV=hepatitis C virus; LLoQ=lower limit of quantification; RNA=ribonucleic acid

For subjects enrolled prior to AM 03, durability of virologic response will be assessed in all subjects who are HCV RNA <LLoQ (either TND or TD[u]) on Day 1 of entry into this protocol and excluding any subject who is TND/TD(u) due to having received an anti-viral treatment after having failed previous therapy in the parent study.

Failure of therapy due to relapse more than 24 weeks after the end of therapy (termed late relapse) in this group of subjects will be measured as an HCV RNA that is confirmed to be ≥LLoQ and is not due to a new infection or re-infection. Confirmation is defined as an HCV RNA that is target detected, quantifiable (TD[q]) from a separate blood draw repeated in approximately 4 weeks.

Subjects who entered this protocol with HCV RNA TND or TD(u) and without confirmation of having failed therapy in the prior treatment study will be categorized as maintaining SVR. These subjects will be assessed for late relapse at every visit in this protocol, including the entry visit. See [Table 2](#) below for actions and interpretations based on HCV RNA results of scheduled and viral confirmation visits.

Table 2

Actions and interpretations based on HCV RNA results of scheduled and Viral Confirmation visits

Scheduled Visit Result	Action	Result of Viral Confirmation	Interpretation
TND	None	N/A	SVR
TD(u)	None	N/A	SVR
TD(q) Not previously determined to be a relapse, e.g. first time HCV RNA \geq LLoQ	Viral Confirmation Visit	TND/TD(u)	SVR
		\geq TDq	Relapse

HCV=hepatitis C virus; LLoQ=lower limit of quantification; RNA=ribonucleic acid; SVR=sustained virologic response; TND=target not detected; TD(q)=target detected, quantifiable; TD(u)=target detected, unquantifiable

Any relapse subject with HCV RNA \geq 1000 IU/mL will have a sequence analysis performed on all samples where HCV RNA \geq 1000 IU/mL.

Viral Resistance Measurements

A viral resistance sample will be collected for every subject at every visit. For subjects with HCV RNA \geq LLoQ (TD[q]) sequence analysis will be performed if HCV RNA \geq 1000 IU/mL.

2.6 LIST OF SAFETY MEASUREMENTS

2.6.1 Adult Population

The long-term safety will be assessed by twice yearly study visits. Once yearly, there will be a directed physical exam and standard laboratory safety tests. Twice yearly, there will be a collection of ECIs (as specified in Section 3.4.3.2), any adverse events (AEs) related to protocol-specified procedures (blood draw), and drug-related serious adverse events (SAEs) as specified in the study flow chart in Section 1.7.1. For details on ECIs collected, see Section 3.4.3.2.

Hematologic/Chemistry Measurements

The following laboratory tests will be performed yearly:

- **Hematology**- hemoglobin (Hgb), hematocrit (HCT), red blood cell (RBC) count, white blood cell (WBC) count, lymphocytes, neutrophils, and platelet count;
- **Chemistry**- alanine aminotransferase (ALT), aspartate aminotransferase (AST), creatinine, alkaline phosphatase, total bilirubin (direct and indirect), urea nitrogen, total protein, albumin, and glucose;
- **Coagulation panel**- including prothrombin time (PT), activated partial thromboplastin time (aPTT), and international normalized ratio (INR) of the prothrombin time; and
- **Computed MELD score**- Sponsor will calculate based on available data for study visit for all adult subjects (at the time of entry in the prior treatment study).

2.6.2 Pediatric Population

The long-term safety will be assessed by twice yearly study visits. Once yearly, there will be a directed physical exam. Twice yearly, there will be a collection of any AEs related to protocol-specified procedures (blood draw) and drug related SAEs as specified in the study flow chart in Section 1.7.2. There are no ECIs or laboratory safety tests collected for the pediatric population.

2.7 STATISTICAL ANALYSIS PLAN SUMMARY

Key elements of the statistical analysis plan (SAP) are summarized below; the comprehensive plan is provided in Section 3.5. The adult population and pediatric population will be summarized separately.

2.7.1 Efficacy Analyses

2.7.1.1 Adult Population

The primary endpoints, primary analysis population, and statistical methods that will be employed for the efficacy analyses in the adult population are presented in [Table 3](#).

There will be no formal efficacy hypothesis testing conducted in this study.

The primary efficacy objectives of this study are to evaluate the durability of response in subjects who achieved SVR in the prior treatment study, as follows, and the evaluation of antiviral resistance to GZR, as described in 2.7.3.

Durability of SVR will primarily be evaluated based upon the time to viral relapse, which is defined as the time from last dose of study therapy taken in the prior treatment study until the date where HCV RNA is \geq LLoQ (see Section 2.5). The analysis population for the time to relapse analysis will be all subjects who achieved SVR during the follow-up

period of the prior treatment study and did not start any new HCV therapy between the end of the prior treatment study and entry in this study.

The distribution of time to viral relapse will be summarized using Kaplan-Meier estimates. In addition, the percentage of subjects who remain HCV RNA <LLoQ during the course of this study will be summarized.

Subjects who receive other treatments for HCV concurrently with this protocol or prior to PN017 and after completion of therapy in the prior treatment study will be discontinued from PN017, and their data excluded from analysis from the time of initiation of new therapy.

Table 3

Summary of Analysis Strategy for Key Efficacy Endpoints
(Adult Population)

Endpoint/Variable	Statistical Method	Analysis Population	Missing Data Approach
Primary:			
Durability of SVR (Time to viral relapse)	Kaplan-Meier plot and summary statistics	All adult subjects entered who achieved SVR in the prior treatment study and who did not start new HCV treatment between end of the prior treatment study and study entry in PN017.	Data as Observed ^a
Antiviral resistance	Descriptive statistics	RAS Analysis Population is defined as allocated adult subjects who met Virologic Failure criteria in the prior treatment study or up to entry into PN017 and who entered PN017 with TD(q) HCV RNA, excluding subjects who were reinfected or who meet any of the following criteria: Failure to receive at least 1 dose of GZR in the prior treatment study or subject had another protocol violation.	Data as Observed
GZR=grazoprevir; HCV=hepatitis C virus; LLoQ=lower limit of quantification; PN=protocol number; RAS=resistance associated substitution(s); RNA=ribonucleic acid; SVR=sustained virologic response			
^a Subjects who discontinue without relapsing will be censored at the time of discontinuation.			

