3.2.2 Concomitant Medication(s)/Treatment(s)

3.2.2.1 Adult Population

In the original protocol, subjects were permitted to participate in other treatment studies for HCV concurrently with this protocol.

Starting with AM 03, subjects are not permitted to receive any therapies used for the treatment of HCV concurrently with this protocol.

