3.3 DURABILITY, VIRAL RESISTANCE, AND SAFETY MEASUREMENTS

3.3.1 Clinical and Laboratory Measurements for Durability, Viral Resistance, and Safety

3.3.1.1 Adult Population

The primary measurement for durability of response in this study is repeat HCV RNA measurements at all study visits. Resistance will be assayed by sequence analysis, and safety will be assessed by directed physical exam, standard laboratory safety tests, and collection of ECIs, any AEs related to protocol-specified procedures (blood draw), and drug related SAE's at each visit as specified in the study flow chart in Section 1.7.1.

Clinical Evaluations

- Directed Physical Examination: Yearly as described in the flow chart.
 - The examination must be performed by the Principal Investigator or Sub-Investigator (physician, physician assistant or nurse practitioner) listed on FDA Form 1572 or *equivalent document*.
- Collection of therapies used for the treatment of HCV: All visits.

NOTE: Following AM 03, all subjects who initiated HCV treatment after enrollment in PN017 were discontinued.

- Childs-Pugh Score: Computed from safety laboratory data and clinical assessment obtained at baseline and every year for adult subjects
 - <http://www.mdcalc.com/child-pugh-score-for-cirrhosis-mortality/>
- Blood pressure and heart rate
- Weight and height

- Review procedure related AEs, ECIs, and drug-related SAEs

Unscheduled Visits:

- Unscheduled visits may be performed at any time at the discretion of the Investigator.

Laboratory Safety Evaluations

The following will be collected (as defined in Section 2.6.1):

- Chemistry (Abbreviated Non-fasting), hematology, and coagulation panel-collected yearly, with an additional collection at 6 months;
- MELD score (with and without dialysis): Computed from safety laboratory data obtained at baseline, and every year for all adult subjects (at the time of entry in the prior treatment study).
- Fibrosure® (Fibrotest®) - collected at 6 months post study entry and then yearly beginning at 12 months in all adult subjects (at the time of entry in the prior treatment study); and
- eGFR (collected yearly in PN052 subjects only).

HCV Evaluations

- HCV RNA quantitation - collected at all visits;

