3.5.3.1 Efficacy and RAS Endpoints

3.5.3.1.1 Adult Population

The primary efficacy endpoint in the adult population is the durability of long-term SVR which will be evaluated based upon the time to viral relapse. Viral relapse is defined as any subject who has confirmed HCV RNA \geq LLoQ and had achieved SVR in the follow-up in the prior treatment study (see Section 2.5). Relapse would be indicated so long as this was the same genotype of the virus seen in the prior treatment study (e.g. not a new infection or re-infection (see Section 2.5). Time to relapse is defined as the time from last dose of study therapy taken in the prior treatment study until the date where HCV RNA is \geq LLoQ. The percentage of subjects who remain HCV RNA $<$ LLoQ during the course of this study will also be estimated.

In adult subjects with HCV RNA \geq 1000 IU/mL at entry or during the study period, HCV sequence analysis will be performed to evaluate the presence of RASs and the persistence of RASs over time.

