3.5.5.1 Statistical Methods for Efficacy Analyses

3.5.5.1.1 Adult Population

The efficacy endpoint of time to viral relapse will be summarized using Kaplan-Meier methodology at fixed time points (6-month intervals). These time points represent the follow-up time since the last dose of study therapy taken in the prior treatment study. Subjects who do not relapse during the current study will be censored on the last visit date. Any subject who relapsed between the end of the prior treatment study and entry into this study will be considered a relapse at the time of study entry.

Relative days ranges, calculated from the date of last dose of therapy taken in the prior treatment study, will be used to define the months of follow-up for the analysis of time to viral relapse. These relative day ranges will be continuous and stretch from the date of last dose in the prior treatment study to the midpoint between the first 2 time points (i.e. 6 and 12 months --> midpoint: 9 months), from midpoint to midpoint between each successive pair of time points and above the last midpoint for the last time point. As the screening visit could occur within 1-year of the last dose of therapy taken in the prior treatment study for subjects enrolled prior to AM 03, certain subjects may have a follow-up time close to 6 years. Day ranges are therefore defined up to Month 72 and are provided in [Table 7](#).

Table 7

Definition of Months of Follow-up for Time to Relapse Analysis

Month	Relative Day Range ^a
6	1 to 274
12	275 to 456
18	457 to 638
24	639 to 821
30	822 to 1003
36	1004 to 1186
42	1187 to 1368
48	1369 to 1550
54	1551 to 1733
60	1734 to 1915
66	1916 to 2098
72	≥ 2098

^a Day range relative to date of last dose of therapy taken in the prior treatment study.

Missing Values

Only observed data will be included in the analyses. For the time to relapse analysis, subjects missing an HCV RNA evaluation at any particular visit will be considered a non-relapser for that visit. Subjects who discontinue the study without relapsing will be censored at the time of discontinuation.

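### SVR subjects who start new HCV therapy before a relapse is confirmed in the study are censored as non-relapsers, which can understate late relapse; a sensitivity analysis should show by how much

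*Combined protocol and SAP*

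**What the plan says.** - **Event.** Section 2.5 requires a quantifiable HCV RNA confirmed "from a separate blood draw repeated in approximately 4 weeks" and not due to new infection or re-infection. Section 3.5.3.1.1 adds: "Relapse would be indicated so long as this was the same genotype of the virus seen in the prior treatment study".
- **New therapy.** Section 2.7.1.1: subjects who take other HCV treatment "will be discontinued from PN017, and their data excluded from analysis from the time of initiation of new therapy". Section 3.5.5 summarizes data after therapy start separately.
- **Censoring.** Table 3, footnote a: "Subjects who discontinue without relapsing will be censored at the time of discontinuation". Section 3.5.5.1.1 repeats this and also says: "Subjects who do not relapse during the current study will be censored on the last visit date".
- **Missing results.** Section 3.5.5.1.1: "subjects missing an HCV RNA evaluation at any particular visit will be considered a non-relapser for that visit".
- **Opportunity for therapy.** Section 3.2.2.1: "In the original protocol, subjects were permitted to participate in other treatment studies for HCV concurrently with this protocol". This ended with Amendment 03.
- **Data available.** Section 3.3.1.1: "Collection of therapies used for the treatment of HCV: All visits".
- **Analysis population.** Section 2.7.1.1 and Table 3 leave out subjects who began new HCV therapy between the prior study and PN017 entry. Section 3.5.4.1.1 leaves out anyone given new HCV therapy after the grazoprevir regimen, with no end date.

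**The concern.** Kaplan-Meier estimation assumes that a subject censored at a given time has the same later relapse risk as those still followed. A subject with SVR would not ordinarily be given HCV therapy unless virus had been found again. Censoring at that moment therefore removes subjects whose risk of having relapsed is far above that of the subjects who remain. Late relapse after SVR is expected to be rare, so a few such subjects could move the primary durability estimate noticeably, and always towards better durability. No section makes new therapy an event, and none plans a sensitivity analysis.

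**Working it through.** The plan states no sample size, expected event count or relapse rate, so there is no figure to reproduce. The check has three parts.

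**1. Trace of the rules.** HCV RNA is drawn every 6 months, with visit windows of ±3 months (Section 1.7.1). Two paths lead to the same result.

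- *Path A.* The last study HCV RNA is below LLoQ. Virus is then found outside the study and therapy starts before the next study sample. There is no study event. Any sample after therapy start is excluded under Section 2.7.1.1. The subject is censored, whichever of the two dates in Section 3.5.5.1.1 is used.
- *Path B.* A first study sample is quantifiable, but therapy starts before the confirming draw (about 4 weeks later in Section 2.5; a return within 14 days in Section 3.3.1.1). The confirming sample would be excluded, so no confirmed event exists and the subject is again censored.

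If both samples precede therapy, the event is already established and only later data are removed. That relapse counts.

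Section 3.5.5.1.1 does recover relapses that occurred between the prior study and PN017 entry, counting them at entry. It has no equivalent rule for relapses between PN017 visits.

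**2. Illustration of size.** All inputs are assumptions: 1000 SVR subjects, six 6-month intervals, true 36-month relapse risk R with constant hazard, and a share q of true relapses treated before confirmation and censored at the previous visit. For simplicity the clock starts at study entry.

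- Hazard per interval: h = 1 − (1 − R)^(1/6).
- Per interval with n at risk: counted events d = n·h·(1 − q); lost relapses c = n·h·q.
- Planned estimate: 1 − [1 − d/(n − c)]^6 = 1 − [1 − h(1 − q)/(1 − hq)]^6, which is close to (1 − q)·R.

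Example with R = 1% and q = 25%: h = 1 − 0.99^(1/6) = 0.001674; h(1 − q)/(1 − hq) = 0.001255/0.999582 = 0.001256; estimate = 1 − (1 − 0.001256)^6 = 0.75%.

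The table gives the planned 36-month estimate, with relapses lost per 1000 subjects in brackets.

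| True R | q = 10% | q = 25% | q = 50% |
|---|---|---|---|
| 0.5% | 0.45% (0.5) | 0.38% (1.25) | 0.25% (2.5) |
| 1% | 0.90% (1.0) | 0.75% (2.5) | 0.50% (5.0) |
| 2% | 1.80% (2.0) | 1.50% (5.0) | 1.01% (10.0) |

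**3. Error in the other direction.** Suppose every therapy start counted as relapse. With R = 1%, re-infection risk r, and a share f of re-infections entering this way, the estimate is about R + r·f:

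- r = 0.5%, f = 25%: 1% + 0.125% = 1.125%.
- r = 0.5%, f = 50%, or r = 1%, f = 25%: 1% + 0.25% = 1.25%.
- r = 1%, f = 50%: 1% + 0.5% = 1.5%.

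Neither treatment of these subjects is unbiased.

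**The case against.** The strongest reply is that the endpoint is relapse, not return of virus. Re-infection is deliberately excluded, and Section 3.3.1.1 genotypes the first quantifiable sample to separate the two. The subjects at issue often have no study sample to genotype, so counting their therapy start as relapse drops both the confirmation and the re-infection requirement. This stands, and it is why the primary event should not be redefined.

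Three stronger inferences are tempting, and the documents do not support them.

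- *Every SVR subject who starts therapy is lost as an event.* Section 2.7.1.1 excludes data only from therapy start, so relapses confirmed earlier remain.
- *The censored subjects are, in the main, relapsers.* The large documented source of early censoring is administrative: after Amendment 03, non-PN052 subjects who had entered below LLoQ were discontinued at their next visit (Sections 1.3.1 and 3.2.4.8.1).
- *Late relapse is understated by some definite fraction.* Any such figure rests on invented counts. Section 3.2.2.1 shows that concurrent HCV treatment was allowed, not that responders used it.

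There are partial safeguards. Unscheduled visits may take place at any time, and final-visit procedures, including HCV RNA, are done at discontinuation. Neither is tied to therapy start, so they narrow the gap without closing it. Data after therapy remain visible in a separate summary. The study tests no hypothesis, so the harm is a biased estimate rather than a false claim of significance.

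**Conclusion.** The concern holds for one group: SVR subjects who start new HCV therapy during PN017 before relapse is confirmed by study samples. For them censoring is informative, and the bias in the primary durability estimate runs towards too little relapse, by roughly the share q of true relapses handled this way. The documents give neither q nor the relapse risk, so the table above shows only a range under stated assumptions. Exposure was widest before Amendment 03. Those responders' data stay in the analysis (Section 1.3.1), and PN052 subjects are followed for 5 years.

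A related inconsistency needs correcting in any case. Read literally, Section 3.5.4.1.1 removes even a confirmed relapser who is later retreated, which Section 2.7.1.1 and Table 3 do not do.

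**What to change.** 1. **Primary analysis.** Keep confirmed relapse, excluding re-infection, as the event.
2. **Sensitivity analysis.** In Section 3.5.5.1.1 and Table 3 footnote a, add a second Kaplan-Meier analysis. In it, an SVR subject who starts new HCV therapy during PN017 without documented re-infection counts as a relapse, dated at the first study HCV RNA at or above LLoQ or, if there is none, at therapy start. Data after therapy start stay excluded.
3. **Reporting.** Give the number of such subjects beside the primary estimate.
4. **Population.** Limit the new-therapy exclusion in Section 3.5.4.1.1 to therapy started before PN017 entry, as in Section 2.7.1.1 and Table 3.
5. **Reconcile.** Section 3.5.5.1.1 gives two censoring dates. Section 3.5.5 still describes concurrent HCV treatment as permitted, against Section 3.2.2.1 from Amendment 03 onwards.

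**Cost.** One extra run, a count, and revised wording. The analysis plan is part of the protocol, and Section 3.5 calls for an amendment when methods for primary objectives change, so the text belongs in an amendment. Adult HCV therapy is already collected at all visits. No outside HCV RNA is needed, and no section collects it.

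**Limits.** Some unrecognised re-infections will count as relapse in the sensitivity run, so the two results should be read as a range. A subject who starts therapy and attends no further visit may be missed by both.
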